# 7.1.1. Interruption of Study Intervention

After randomization, the investigator may interrupt study drug, for example, due to an AE (e.g., nausea and vomiting), or a clinically significant laboratory value. If study drug interruption is due to an AE, the event is to be followed and documented. Every effort should be made by the investigator to maintain patients in the study and to restart study drug promptly after any interruption, as soon as it is safe to do so (See Section 7.1.2 for restarting study drug). The dates of study drug interruption and restart must be documented. The data related to interruption of study treatment will be documented in source documents and entered on the eCRF. Patient noncompliance should not be recorded as interruption of study drug on the eCRF.

# 7.1.2. Restarting Study Drug after Interruption

If the number of consecutive missed doses is  $\leq 2$ , the treatment can be restarted at the same dose, if the drug was well-tolerated prior to discontinuation.

- If the number of consecutive missed doses is ≥3, then the treatment should be restarted at 5 mg irrespective of the dose the patient was receiving before the interruption and subsequently follow the original dose escalation scheme (i.e., beginning at 5 mg with 2.5 mg dose increments every 4 weeks to reach the assigned dose level). See Section 6.6 for guidance on dose escalation/maintenance for patients who do not tolerate a dose level of tirzepatide.
- The investigator will use the IWRS to receive the appropriate study drug dispensing information to preserve blinding of the study drug

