### 4. Study Design

# 4.1. Overall Design

Study GPHR is a Phase 2, multicenter, randomized, double-blinded, placebo-controlled study that will investigate the effects of treatment with tirzepatide 5 mg, 10 mg and 15 mg SC QW compared with placebo on NASH resolution with no worsening of fibrosis in patients with biopsy-proven NASH and fibrosis, with or without T2DM.

Four intervention groups will be studied:

- Tirzepatide 5 mg SC QW, initially 2.5 mg SC QW for 4 weeks then 5 mg SC QW
- Tirzepatide 10 mg SC QW, initially 2.5 mg SC QW then dose escalated by 2.5 mg every 4 weeks until target dose is reached
- Tirzepatide 15 mg SC QW, initially 2.5 mg SC QW then dose escalated by 2.5 mg every 4 weeks until target dose is reached
- Placebo

All participants will receive diet and physical activity counseling throughout the study.

Study GPHR will consist of 3 periods:

- Screening (Visits 1 and 2)
- Treatment (Visits 3 to 14)
  - 4- to 20-week dose escalation (4-week for 5 mg group, 12-week for 10 mg group, 20-week for 15 mg group)
  - o 32- to 48-week maintenance (48-week for 5 mg group, 40-week for 10 mg group, 32-week for 15 mg group)
- Safety follow-up (4 weeks post-treatment, through Visit 801)

The maximum total duration of the combined treatment periods is 52 weeks.

The approximate maximum total duration of study participation for each participant, including screening and post-treatment follow-up periods, is 68 weeks. Some participants may require additional follow-up after V801 for evaluation of treatment-emergent antidrug antibodies (ADA).

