### 4.2. Scientific Rationale for Study Design

Study GPHR is a Phase 2 study designed to examine the efficacy and safety of QW tirzepatide compared with placebo in patients with biopsy-proven NASH and fibrosis. Body weight and NASH biomarker data from the tirzepatide Phase 2 study in T2DM (GPGB; Section 2.2) provide a strong rationale for development of tirzepatide as a potential treatment for NASH.

Inclusion of a placebo comparator in Study GPHR will allow for a direct comparison of the safety and efficacy of tirzepatide in patients with NASH over a 12-month time period. The currently recommended treatment for NASH is diet and exercise in order to reduce body weight. All patients will receive diet and exercise counseling (See Appendix 6, Section 10.6), thus placebo patients will be receiving the recommended treatment for NASH. Although some Phase 2 studies of other compounds being investigated for treatment of NASH have had treatment durations less than 12 months, a treatment duration of 52 weeks was chosen because of the need for a 20-week dose escalation period for the 15 mg dose of tirzepatide. This slow dose escalation approach was chosen to minimize gastrointestinal (GI) side effects of tirzepatide, which were common in the Phase 2 T2DM study that included a shorter dose escalation period (6 weeks to reach 15 mg SC QW). Thus, the 52-week treatment period will be sufficient to compare the effects of tirzepatide and placebo to resolve NASH. Several noninvasive methods to evaluate NASH and fibrosis, utilizing serum biomarkers and imaging modalities, have been included in the study with the objective of developing future alternatives to liver biopsy for diagnosis of NASH and evaluation of treatment effects of tirzepatide in patients with NASH. The data from this study will inform the decision of whether to continue evaluation of tirzepatide in Phase 3 studies for treatment of NASH.

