### 6.5.2. Management of Participants with Gastrointestinal Symptoms

In the Phase 2 program, the most commonly reported treatment-emergent adverse events (TEAEs) for participants receiving tirzepatide were nausea, vomiting, and diarrhea. To mitigate GI symptoms and manage participants with intolerable GI AEs, the investigator should:

- Advise patients to eat smaller meals, for example, splitting 3 daily meals into 4, or more smaller meals, and to stop eating when they feel full. Also, patients may be informed that lower-fat meals could be better tolerated.
- Prescribe symptomatic medication (for example, anti-emetic or antidiarrheal medication) per local country availability and individual patient needs. Use of symptomatic medication should be captured as concomitant medication in the eCRF.
- Temporarily interrupt study drug (omit 1 dose, the patient will take 3 of 4 doses at that dose level). The data related to temporary interruption of study treatment should be documented in source documents and entered on the eCRF.
- After the interruption, restart at the same dose with the patient taking medication to alleviate their GI symptoms.

If intolerable GI symptoms or events persist despite the above measures, see Section 6.6.

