### 6.6. Dose Modification

Patients who do not tolerate the first dose escalation, in other words from 2.5 mg to 5 mg (or placebo equivalent), will need to discontinue from study treatment. If a patient does not tolerate a dose level higher than 5 mg for 2 weeks (e.g., moderate-to-severe nausea, vomiting, or diarrhea) and the investigator does not believe that the patient will tolerate the dose with further exposure, then the investigator may reduce the dose to the next lower 5 mg incremental dose (e.g., 5 mg or 10 mg). If this dose is tolerated after 4 weeks, the dose should be increased by 2.5 mg every 4 weeks until the target dose is achieved. If this dose escalation is not tolerated, the dose should be reduced to the next lower 5 mg incremental dose that was tolerated (e.g., 5 mg or 10 mg). The patient will remain at that dose level for the duration of the study. Maintenance doses of 2.5 mg, 7.5 mg, or 12.5 mg will not be allowed.

In order to maintain blinding of the investigator and patient, the investigator should call the IWRS to explain that the patient needs the dose reduced and IWRS will provide dispensing information. Dose reductions may occur at unscheduled visits.

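### The 5 mg restart after three or more missed doses (Protocol 7.1.2) makes no exception for participants who have taken only one or two 2.5 mg doses

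*Protocol*

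**What the plan says.** Every tirzepatide arm starts at 2.5 mg weekly in Weeks 0 to 3 and moves to 5 mg at Week 4 (Protocol Section 6.1). For the lowest arm, Section 4.1 puts it as "Tirzepatide 5 mg SC QW, initially 2.5 mg SC QW for 4 weeks then 5 mg SC QW". Section 4.2 gives the reason: "This slow dose escalation approach was chosen to minimize gastrointestinal (GI) side effects of tirzepatide". Section 4.3 adds that starting at 2.5 mg with four-week steps gives time for GI tolerance to develop.

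Section 7.1.2 has two restart rules.

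- After at most two consecutive missed doses, "the treatment can be restarted at the same dose, if the drug was well-tolerated prior to discontinuation".
- After three or more, "the treatment should be restarted at 5 mg irrespective of the dose the patient was receiving before the interruption", followed by 2.5 mg steps every four weeks up to the assigned dose. This rule has no tolerability condition of its own, although it points to Section 6.6 for participants who do not tolerate a dose level.

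Three other sections bear on the point.

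- Section 7.1.1 names nausea and vomiting as examples of reasons to interrupt, and asks the investigator to "restart study drug promptly after any interruption, as soon as it is safe to do so". That leaves the timing of a restart to judgement, but not the dose.
- Section 6.5.2 handles GI symptoms with a short interruption: "omit 1 dose, the patient will take 3 of 4 doses at that dose level".
- Section 6.6 covers intolerance of the first escalation: such participants, going "from 2.5 mg to 5 mg (or placebo equivalent), will need to discontinue from study treatment". It also says "Maintenance doses of 2.5 mg, 7.5 mg, or 12.5 mg will not be allowed".

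None of Sections 6.5.2, 6.6, 7.1.1, 7.1.3 or 8.3.7.10 makes an exception to the 5 mg restart for someone still on 2.5 mg.

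**The concern.** The long-gap rule is plainly built for participants on higher doses, where returning to 5 mg is a step down. For a participant interrupted after one or two 2.5 mg doses it is a step up, to a dose never taken before. It comes after a gap of at least three weekly doses that may itself have been caused by GI events. After the same one or two doses, a shorter gap resumes 2.5 mg, and only if that dose was well tolerated.

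Two things are at stake. The first is tolerability: the run-in is meant to build GI tolerance, and these participants have had only part of it. The second is retention: under Section 6.6, failure at 5 mg ends study treatment, because no reduction to 2.5 mg is available. Under Section 8.1.1, a participant who stops study drug before Week 36 has no second biopsy, and under SAP Section 3.4 a participant without a post-baseline biopsy is left out of the primary analysis. An avoidable early stop therefore also removes a participant from the main comparison.

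**Working it through.** The documents contain no figure to reproduce on this point. The check sets the restart rules against the weekly schedule.

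**Inputs.** Doses are weekly from Week 0, with none at Week 52 (Protocol Section 1.3). The scheduled dose is 2.5 mg in Weeks 0 to 3 and 5 mg from Week 4 (Section 6.1). The restart rules are those of Section 7.1.2.

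**Step 1: direction of the long-gap rule at each level.** Ratio = 5 mg / last dose.

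| Last dose (mg) | 2.5 | 5 | 7.5 | 10 | 12.5 | 15 |
|---|---|---|---|---|---|---|
| Ratio | 2.0 | 1.0 | 0.67 | 0.50 | 0.40 | 0.33 |

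Only at 2.5 mg does the rule raise the dose. The scheduled step from 2.5 to 5 mg has the same ratio of 2.0, so the ratio alone is not the problem. What differs is how much 2.5 mg dosing comes before it.

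**Step 2: the affected paths.** Restart week = doses taken + doses missed.

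| 2.5 mg doses taken | Doses missed | Restart week | Restart dose | Scheduled dose that week | Cumulative mg before restart |
|---|---|---|---|---|---|
| 1 | 2 | 3 | 2.5 mg | 2.5 mg | 2.5 |
| 1 | 3 | 4 | 5 mg | 5 mg | 2.5 |
| 2 | 2 | 4 | 2.5 mg | 5 mg | 5 |
| 2 | 3 | 5 | 5 mg | 5 mg | 5 |

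The plan gives 4 × 2.5 = 10 mg before the first 5 mg dose. One dose taken means three of four run-in doses lost (75%); two taken means two of four lost (50%). In neither case is 5 mg earlier than scheduled.

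**Step 3: drug on board at the restart.** The half-life is not stated. Section 8.2.4.1 treats the Visit 801 sample as taken five half-lives after treatment, which suggests roughly 5 to 7 days; I take that range as an assumption. With simple exponential decay, residual = sum of 2.5 × 0.5^(days since dose / half-life).

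- Just before a 5 mg restart after exactly three missed doses: 0.05 mg (one dose taken, 5 days) to 0.23 mg (two doses taken, 7 days).
- Just before the planned first 5 mg dose: 1.5 mg (5 days) to 2.3 mg (7 days).

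So little of the run-in drug remains at the restart. This cuts both ways: adding the 5 mg dose, the total is about 5.05 to 5.23 mg at a restart, against 6.5 to 7.3 mg at the planned step. The restart does not produce a higher level than the plan. The issue is less prior adaptation, not more drug.

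**Step 4: cost of a 2.5 mg restart.** Weeks at target = 52 − restart week − weeks to reach target. From a 5 mg restart, target is reached after 0, 8 and 16 weeks in the 5, 10 and 15 mg arms. With four weeks at 2.5 mg first, it is reached after 4, 12 and 20.

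| Restart week | Current rule (5/10/15 mg arms) | With 2.5 mg for 4 weeks first |
|---|---|---|
| 4 | 48/40/32 | 44/36/28 |
| 5 | 47/39/31 | 43/35/27 |

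The loss is four weeks throughout, from 4/48 = 8.3% to 4/31 = 12.9%. These are the earliest restarts. A longer gap shortens both columns equally and leaves the four-week difference, which then becomes a somewhat larger share.

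**The case against.** The strongest reply is that this is a clear rule and a legitimate sponsor choice. Going from 2.5 to 5 mg is the step every tirzepatide participant takes, and 5 mg is the calendar dose from Week 4. A single restart dose is simple to run through a blinded IWRS. Restarts happen only when the investigator thinks it safe, the GI measures of Section 6.5.2 stay available, and the stopping rule in Section 6.6 applies to everyone at that step. Because the GI route omits one dose only, a gap of three or more this early should be uncommon. All of that stands, and it keeps the point small.

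Two further objections also stand in part.

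- A reader might take the three-of-four wording in Section 6.5.2 as a minimum before 5 mg. It is not: it describes the result of omitting one dose. If escalation follows the calendar after a short gap, which Section 7.1.2 does not settle, a participant dosed at Week 0 who misses Weeks 1 and 2 resumes 2.5 mg at Week 3 and reaches 5 mg at Week 4, after two 2.5 mg doses.
- The contrast between a short and a long gap may be brief. After two doses, missing two resumes 2.5 mg at Week 4 and missing three gives 5 mg at Week 5; if the calendar applies, both participants are on 5 mg at Week 5.

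What these replies do not answer is the missing exception. Being on calendar does not supply the doses that were not taken, and discretion over when to restart does not extend to the restart dose.

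**Conclusion.** The point holds as a cheap improvement of low severity. Section 7.1.2 sends participants with one or two 2.5 mg doses to 5 mg after a long gap, having lost 75% or 50% of the run-in, with discontinuation as the only outcome if 5 mg is not tolerated. That sits badly with the reasoning in Sections 4.2 and 4.3.

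A reader might infer that the rule gives a dangerous or premature doubling, or that it threatens the trial's result. The documents support neither. The dose is not ahead of the Section 6.1 schedule, and nothing measures how one or two fewer 2.5 mg doses change tolerability. The number affected is not given and may be zero, and with 1:1:1:1 randomization about a quarter of any such participants would be on placebo. No power, alpha or sample size figure moves.

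The conclusion rests on the wording of Section 7.1.2 and the Section 6.1 schedule. The half-life range in the working is an assumption, and the conclusion does not depend on it. Participants who took three or four 2.5 mg doses are outside the point.

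**What to change.** Add to the second rule of Section 7.1.2: *after three or more consecutive missed doses, participants who have taken fewer than three 2.5 mg doses (or placebo equivalent) restart at 2.5 mg for 4 weeks and then escalate as in Section 6.1; all others restart at 5 mg.* Set the IWRS to match.

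The cut-off of three is a practical choice in line with Section 6.5.2, and the protocol sets no such floor. The four weeks are a lead-in, so the bar on 2.5 mg as a maintenance dose is respected. All three tirzepatide arms begin at 2.5 mg, so such a restart does not reveal the dose arm. The sentence does not settle how escalation proceeds after a short gap.

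The cost is one protocol sentence, one IWRS setting and, for affected participants only, the four weeks at target dose shown above.

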### 7.1.3. Interruption/Discontinuation due to a Hepatic Event or Liver Test Abnormality

Participants who are interrupted/discontinued from investigational product due to a hepatic event or liver test abnormality should have additional hepatic safety data collected via case report form (CRF).

Interruption/discontinuation of the investigational product for abnormal liver tests should be considered by the investigator when a participant meets one of the following conditions after consultation with the Lilly-designated medical monitor. These criteria differ based on the baseline liver test findings and are summarized below (Regev et al. 2019). If study drug is interrupted, it can be restarted only if another etiology is identified and liver enzymes return to baseline.

### For participants with baseline ALT <1.5 X ULN and normal baseline bilirubin:

- ALT or AST >8 X ULN
- ALT or AST >5 X ULN for more than 2 weeks
- ALT or AST >3 X ULN and total bilirubin level (TBL) >2 X ULN or INR >1.5
- ALT or AST >5 X ULN with the appearance of fatigue, nausea, vomiting, right upper-quadrant pain or tenderness, fever, rash, and/or eosinophilia (>5%)
- ALP >3 X ULN
- ALP >2.5 X ULN and TBL >2 X ULN
- ALP >2.5 X ULN with the appearance of fatigue, nausea, vomiting, right quadrant pain or tenderness, fever, rash, and/or eosinophilia (>5%)

# For participants with baseline ALT $\geq$ 1.5 X ULN and normal baseline bilirubin:

- ALT >5 X baseline or  $\geq$ 500 U/L (whichever occurs first)
- ALT >2 X baseline or  $\ge$ 300 U/L (whichever occurs first) and TBL >2 X ULN
- ALT >3 X baseline or ≥300 U/L (whichever occurs first) with the appearance of fatigue, nausea, vomiting, right upper-quadrant pain or tenderness, fever, rash, and/or eosinophilia (>5%)
- ALP >3 X ULN
- ALP >2.5 X ULN and TBL >2 X ULN
- ALP >2.5 X ULN with the appearance of fatigue, nausea, vomiting, right quadrant pain or tenderness, fever, rash, and/or eosinophilia (>5%)

# 7.2. Participant Discontinuation/Withdrawal from the Study

Participants will be discontinued in the following circumstances:

- Enrollment in any other clinical study involving an investigational product or enrollment in any other type of medical research judged not to be scientifically or medically compatible with this study
- Participation in the study needs to be stopped for medical, safety, regulatory, or other reasons consistent with applicable laws, regulations, and good clinical practice (GCP)
- Investigator decision
  - the investigator decides that the participant should be discontinued from the study
  - o if the participant, for any reason, requires treatment with another therapeutic agent that has been demonstrated to be effective for treatment of the study indication, discontinuation from the study occurs prior to introduction of the new agent
- Participant decision
  - o the participant or the patient's designee, (for example, parents or legal guardian) requests to be withdrawn from the study

Participants discontinuing from the study prematurely for any reason should complete AE and other safety follow-up per Section 1.3 (Schedule of Activities), Section 8.3 (Adverse Events and Serious Adverse Events), and Section 8.2 (Safety Assessments) of this protocol.

# 7.2.1. Discontinuation of Inadvertently Enrolled Patients

If the sponsor or investigator identifies a participant who did not meet enrollment criteria and was inadvertently enrolled, then the patient should be discontinued from study treatment.

# 7.3. Lost to Follow-Up

A participant will be considered lost to follow-up if he or she repeatedly fails to return for scheduled visits and is unable to be contacted by the study site. Site personnel are expected to make diligent attempts to contact participants who fail to return for a scheduled visit or were otherwise unable to be followed up by the site.

Site personnel, or an independent third party, will attempt to collect the vital status of the participant within legal and ethical boundaries for all participants randomized, including those who did not get investigational product. Public sources may be searched for vital status information. If vital status is determined, this will be documented and the participant will not be considered lost to follow-up.

Lilly personnel will not be involved in any attempts to collect vital status information.

Discontinuation of specific sites or of the study as a whole are handled as part of Section 10.1.7.2.

# 8. Study Assessments and Procedures

Unless otherwise stated in the subsections below, all samples collected for specified laboratory tests will be destroyed within 60 days of receipt of confirmed test results. Certain samples may be retained for a longer period, if necessary, to comply with applicable laws, regulations, or laboratory certification standards.

Study procedures and their timing are summarized in the SoA (Section 1.3). Protocol waivers or exemptions are not allowed.

Immediate safety concerns should be discussed with the sponsor immediately upon occurrence or awareness to determine if the participant should continue or discontinue study intervention.

Adherence to the study design requirements, including those specified in the SoA, is essential and required for study conduct.

All screening evaluations must be completed and reviewed to confirm that potential participants meet all eligibility criteria. The investigator will maintain a screening log to record details of all participants screened and to confirm eligibility or record reasons for screening failure, as applicable.

Procedures conducted as part of the participant's routine clinical management (e.g., ophthalmic exam) and obtained before signing of the ICF may be utilized for screening or baseline purposes provided the procedures met the protocol-specified criteria and were performed within the time frame defined in the SoA.

Repeat or unscheduled samples may be taken for safety reasons or for technical issues with the samples.

# 8.1. Efficacy Assessments

# 8.1.1. Primary Efficacy Assessment

The primary efficacy measurement in this study is NASH resolution with no worsening of fibrosis based on liver histology at Week 52 compared with baseline.

In alignment with United States (US) Food and Drug Administration (FDA) draft guidance (FDA 2018) and the EMA reflection paper (EMA 2018), NASH resolution will be defined as:

- absence of fatty liver disease or simple steatosis without steatohepatitis;
- the absence of hepatocellular ballooning (NAS 0 for ballooning)
- with or without mild lobular inflammation (NAS 0 or 1 for inflammation), and
- any value for steatosis.

No worsening of fibrosis will be defined as no increase in fibrosis stage from baseline to Week 52.

Liver histology will be evaluated via liver biopsies collected at baseline in participants for whom a liver biopsy of adequate quality performed within 6 months of screening is unavailable, and at Week 52 (end-of-treatment) in all participants who remained on study drug. Patients who discontinued study drug prior to Week 36 will not have a second liver biopsy.

Histology will be scored according to the NASH CRN guidelines (Kleiner et al. 2005; Puri and Sanyal 2012). Pathologists reviewing the liver biopsies will be blinded to treatment group. Intra- and inter-observer variability in assessment of histology will be assessed. The glass slides may be scanned to facilitate future additional exploratory analyses of the whole slide images.

Liver biopsy tissue block and slides will be retained at a facility selected by Lilly or its designee for a maximum of 15 years after the last participant visit for the study, or for a shorter period if local regulations and ERBs impose shorter time limits. This retention period enables use of new technologies, response to regulatory questions, and investigation of variable response that may not be observed until later in the development of tirzepatide or after tirzepatide becomes commercially available.

